9.1.1.3. Adverse Event Severity or Relationship to Study Drug

If the severity of an AE is not reported, then for tables of AEs by severity, the event will be classified as ‘Severe’ and will be footnoted for the table to indicate this imputation. If the relationship to study treatment is not reported for an AE, then for tables of study-drug related AEs, the event will be assigned the relationship of ‘definite’. Tables presenting related AEs will include all AEs with relationships of ‘possible’, ‘probable’ or ‘definite’ as assessed by the investigator.

9.2. Subject Disposition

Subject disposition summaries will include the number of subjects

- Randomized
- Completed Study, with reason for termination

The safety analysis set and enrollment data will be presented as treated. All other data will be presented as randomized.

The disposition summary will present the data for each treatment group.

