Subjects who withdraw from the study before the study treatment procedure may be replaced. Once a subject number is assigned, subject numbers will not be reused; subjects enrolled to replace those who withdraw will be assigned a unique subject number and randomized to treatment according to the procedures outlined above.

Subjects who are randomized but are withdrawn from the study before receiving the study treatment procedure may be replaced. Additionally, subjects may be replaced if insufficient and/or incomplete data are noted on safety or clinical outcomes.

Diagnostic Medial Branch Block (MBB)

As part of the eligibility criteria, subjects must have undergone two successful diagnostic medial branch blocks consisting of two positive blocks with local anesthetic only (i.e., no steroids) under fluoroscopic guidance that results in at least 50% relief of primary (index) pain for the duration of the local anesthetic used.

iovera° Medial Branch Block

ioveraº Treatment

The iovera° system consists of a reusable, portable Handpiece, along with single patient use sterile Smart Tips (i.e., cryoprobes) and disposable nitrous oxide (N₂O) cartridges. The iovera° system produces the desired effect through initiation of a cooling cycle. Each cooling cycle is initiated by fully inserting the Smart Tip into the selected procedure site and activating the cryogen flow. The Smart Tip needles are made of stainless steel and have a closed tip, fully enclosing the cryogen. The "190" Smart Tip will be used in this study.

Administration Technique

iovera° is to be administered in the lumbar spine at the target medial branch nerves encompassing one level above and below the involved vertebral levels.

Subjects will receive a fluoroscopic guided iovera^o medial branch block. Blocks will be performed with the subject in the prone position under asepsis in the following manner:

- Record start time of procedure
- The investigator injects 1% Lidocaine at the treatment site to numb the skin and tissue around the facet joint
- The iovera° Smart Tip is positioned appropriately and a fluoroscopic image is taken to confirm the Tip's position
- The iovera^o Smart Tip is inserted through the skin wheal to the target medial branch nerve below the junction of the superior articular and transverse process

Name of Device:

iovera° System

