6. STUDY OVERVIEW

[figure not shown]
This is a single-center, randomized, pilot study in adult subjects with facet-mediated CLBP. Thirty (30) subjects are planned for initial enrollment and will be randomized 1:1 to receive iovera^o medial branch cryoneurolysis or radiofrequency ablation.

This study is designed to determine if a full efficacy RCT can be successfully conducted using the procedures and protocols described in the current pilot study protocol, or if protocol modifications are necessary before moving forward with a full efficacy RCT. Furthermore, the study will assess the feasibility of the outcome measurements employed, construct a foundation for sample size calculation, and the acceptability/practicality of conducting the full efficacy RCT.

Randomization to treatment groups according to the randomization assignment will be performed on the day of treatment. The treatment groups are:

- **Group 1:** subjects will receive iovera^o cryoneurolysis of the medial branch nerves
- **Group 2:** subjects will receive RFA of the medial branch nerves

Figure 1 Study Schema

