9.4.2. Baseline Characteristics

The summary of baseline characteristic data will present:

- Body Mass Index (BMI) (kg/m²)
- Tabaco use status
- NRS current pain intensity score (pain “average”)
- Duration of having diagnosed with low back pain (years)
- Oswestry Disability Index

Baseline characteristics summaries will present the data for each treatment group. Descriptive statistics (n, mean, SD, median, minimum and maximum) will be provided for continuous variables. The number and percent of subjects will be tabulated for the categorical variables.

Baseline characteristic data will be summarized and listed using the safety analysis set.

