10. SAMPLE SIZE CALCULATIONS

As the aim of this pilot study is not to assess effectiveness or efficacy, formal hypothesis testing will not be determined, and sample size will not be calculated based on desired statistical power to detect a treatment effect. A total of 30 subjects are planned for this pilot study, with 15 randomized to each of the 2 study groups.

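### SAP 9.2 presents enrolment as treated and SAP 9.4.2 puts baseline characteristics in as-treated columns; both should follow randomised arm, and receipt of the assigned treatment should be tabulated

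*SAP*

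**What the plan says.** - SAP 9.2 sets the presentation rule: "The safety analysis set and enrollment data will be presented as treated. All other data will be presented as randomized". The disposition summary is by treatment group and names two items: the number randomised, and the number completing the study with reasons for termination. It has no item for treated, treated as assigned, treated with the other device, or not treated.
- SAP 8 restricts both the safety set and the efficacy set to randomised subjects who were treated. The safety set is grouped by treatment received and the efficacy set by randomised arm.
- SAP 9.4.2, which covers baseline NRS and tobacco status among other items, says: "Baseline characteristic data will be summarized and listed using the safety analysis set".
- SAP 9.4.1 (age, sex, ethnicity, race) names no analysis set.
- SAP 9.7.2 runs efficacy analyses on the efficacy set. The model in SAP 9.7.2.1.1 adjusts for baseline NRS, sex and tobacco status.
- The protocol, under Replacement of Subjects, allows for pre-treatment loss: "Subjects who are randomized but are withdrawn from the study before receiving the study treatment procedure may be replaced".
- SAP 5.1 makes feasibility part of the primary objective. SAP 6 says the pilot is to inform "the acceptability/practicality of conducting the full efficacy RCT".

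**The concern.** Being enrolled and allocated to an arm is settled before any treatment is given, so an as-treated display cannot describe it. A subject who withdraws between assignment and procedure has no as-treated arm. A subject who receives the other device appears as if allocated to it.

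Two things are at stake. First, whether subjects accept and receive the assigned procedure is a natural result for a pilot meant to judge whether a full trial can be run, and no planned table reports it. Second, the baseline table is where a reader checks whether the compared arms were alike. If its columns are as treated while the efficacy model is as randomised, the table may describe slightly different groups from those compared. Sex, the third covariate, sits in the demographics table. That table names no set and would by default be as randomised, so two adjacent tables could have different columns.

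**Working it through.** **Planned figure.** SAP 10: "A total of 30 subjects are planned for this pilot study, with 15 randomized to each of the 2 study groups". At 1:1, 30/2 = 15 per arm, which agrees. SAP 10 also says "sample size will not be calculated based on desired statistical power to detect a treatment effect", so there is no power calculation to reproduce. The check is a count of table columns.

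**Inputs.** 15 randomised per arm (SAP 10); set definitions (SAP 8). The documents give no counts of untreated or crossed-over subjects, so 0 to 2 per arm is assumed. I read the study device in the efficacy-set definition as either study treatment.

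**Formulas.** Let u1 and u2 be the untreated subjects in the iovera and RFA arms, c12 the crossovers from iovera to RFA, and c21 those from RFA to iovera.

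- Safety columns (as treated): iovera = 15 − u1 − c12 + c21; RFA = 15 − u2 − c21 + c12
- Efficacy columns (as randomised): 15 − u1; 15 − u2
- True uptake of the assigned treatment: (15 − u1 − c12)/15; (15 − u2 − c21)/15

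| Assumed case | Safety columns (iovera, RFA) | Efficacy columns | True uptake (iovera, RFA) |
|---|---|---|---|
| A. All treated as assigned | 15, 15 | 15, 15 | 15/15, 15/15 (100%, 100%) |
| B. One crossover each way | 15, 15 | 15, 15 | 14/15, 14/15 (93.3% each) |
| C. Two crossovers each way | 15, 15 | 15, 15 | 13/15, 13/15 (86.7% each) |
| D. Two iovera to RFA only | 13, 17 | 15, 15 | 13/15, 15/15 (86.7%, 100%) |
| E. Two iovera untreated | 13, 15 | 13, 15 | 13/15, 15/15 (86.7%, 100%) |

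For example, case B: the iovera safety column is 15 − 0 − 1 + 1 = 15, and uptake is (15 − 0 − 1)/15 = 93.3%.

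**Reading the table.**

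- Cases A, B and C give identical column totals, so offsetting crossovers cannot be seen in them.
- In case D the net crossover shows, because the safety and efficacy columns differ.
- In case E the two untreated subjects are absent from the baseline table. They can be recovered as 15 − 13 = 2 only if the randomised count is shown by randomised arm. If that count is treated as enrolment data, and so shown as treated, they have no column. SAP 9.2 does not say which applies.

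**Size.** Each untreated or crossed-over subject moves an arm's uptake by 1/15 = 6.7 points. Exact 95% intervals for what an uptake row could report are 78.2 to 100% for 15/15, 68.1 to 99.8% for 14/15, and 59.5 to 98.3% for 13/15.

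**The case against.** The case for leaving the plan alone has several sound parts.

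- **Untreated subjects are not clearly lost.** A reader might infer that they vanish from the report. The documents do not support that: SAP 9.2 does plan a randomised count with reasons for termination. If it is shown as randomised, subtracting the safety-set number gives the untreated number.
- **Uptake is not impossible to report.** That too might be inferred, but SAP 9.1 promises individual listings, and the deviation listing in SAP 9.3 is on the safety set, which includes every treated crossover. It would omit untreated subjects, but the point largely stands: uptake is derivable, just not planned as a summary.
- **SAP 9.4.2 does not contradict SAP 9.2.** One might set it against "All other data will be presented as randomized", but the rule exempts the safety set and baseline is placed on that set. The choice is consistent; the difficulty is the mismatch with the efficacy groups.
- **A figure such as 15/17 = 88.2% shown as 15/15 = 100% should not be relied on.** It assumes two iovera subjects untreated and replaced, and one reading of an undefined row; no planned table displays an uptake percentage.
- **The effect is probably small.** Assignment is on the day of treatment, so there is little time to withdraw. Both sets require treatment, so on the reading above they have the same members and differ only in where a crossover is placed.
- **Some text cannot be seen.** SAP 9.6.4, on study success, is redacted, and the list of outcomes announced under Feasibility Endpoints in the protocol is not visible. Either might address uptake.

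None of this supports the rule itself. "The safety analysis set and enrollment data will be presented as treated" is an explicit instruction for enrolment, and it is the wrong grouping for that purpose.

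**Conclusion.** The point holds in a limited form. Enrolment should not be presented as treated, and baseline characteristics should not sit in columns that can differ from the arms compared for efficacy. Receipt of the assigned treatment is not a planned summary in the visible text and is not always recoverable from the summary tables: one crossover each way would leave every column total at 15 with true uptake at 93.3% per arm, and two each way would do the same at 86.7%.

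These counts are assumptions. If there are no crossovers and no untreated subjects, the effect is nil. No efficacy or safety estimate is shown to change; what is affected is the description of the arms and one feasibility result.

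**What to change.** 1. Amend SAP 9.2 so that enrolment and disposition are shown by randomised arm on all randomised subjects.
2. Add disposition rows for treated as assigned, treated with the other device, and not treated, with the reason and whether the subject was replaced.
3. Show demographics (SAP 9.4.1) and baseline characteristics (SAP 9.4.2) by randomised arm on the efficacy analysis set, so that both describe the groups in the efficacy model.
4. Keep as-treated grouping for the safety tables only.

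The cost is a change of SAP wording and a slightly longer disposition table; no new data collection appears necessary. Reported uptake may look less favourable than it would without these rows.

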9.3. Protocol Deviations

A blinded review before database lock will be conducted to determine important protocol deviations. Protocol deviations are considered important if, based on Sponsor assessment, they can impact the study integrity or interpretability of study results.

Important protocol deviations will also be evaluated if they impact efficacy data. Important protocol deviations with potential impact on efficacy will be used to exclude subjects from the Per-Protocol analysis set.

All protocol deviations will be reviewed and categorized before database lock. All important protocol deviations will be summarized by deviation category (including Inclusion Criteria, Exclusion Criteria, ICF, Concomitant Medication, and other if applicable). The protocol deviation data will also be presented as a by-subject data listing using the safety analysis set.

9.4. Description of Demographics and Baseline Characteristics

9.4.1. Demographic Data

The summary of demographic data will present:

- Age (years) – descriptive statistics
- Sex – n (%)
- Ethnicity – n (%)
- Race – n (%)

The demographic summary will present the data for each treatment group. Demographic data will be summarized overall.

9.4.2. Baseline Characteristics

The summary of baseline characteristic data will present:

- Body Mass Index (BMI) (kg/m²)
- Tabaco use status
- NRS current pain intensity score (pain “average”)
- Duration of having diagnosed with low back pain (years)
- Oswestry Disability Index

Baseline characteristics summaries will present the data for each treatment group. Descriptive statistics (n, mean, SD, median, minimum and maximum) will be provided for continuous variables. The number and percent of subjects will be tabulated for the categorical variables.

Baseline characteristic data will be summarized and listed using the safety analysis set.

9.5. Medical and Surgical History

Medical and surgical history will be summarized by system organ class and preferred term using Medical Dictionary for Regulatory Activities (MedDRA v 26.1) or more recent version.

All medical and surgical history will be included in the data listings.

9.6. Safety Analyses

Safety data will be summarized descriptively by treatment groups and overall. No statistical testing for comparison of treatment groups will be performed for safety variables.

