5. STUDY OBJECTIVES

5.1. Primary Objective

The primary objective of this study is to assess the safety and feasibility of iovera® lumbar medial branch cryoneurolysis vs. radiofrequency ablation (RFA) for facet-mediated chronic low back pain (CLBP).

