9.6.1. Adverse Events

Adverse events will be coded using the Medical Dictionary for Regulatory Activities (MedDRA v 26.1) or more recent version.

A treatment related adverse event will be considered a TEAE if it starts on/after the time of study (iovera^o or RFA) treatment. If an AE has a partial onset date and time, the imputed start dates will be used to determine treatment-emergence (**Section 9.1.1.2**).

All summaries of AEs will include AEs that occur after the start of iovera^o treatment. Events that start prior to iovera^o treatment will be identified in listings only.

AEs will be summarized using subject incidence table. An overview of AEs will be presented. This table will include n (%) of subjects with:

- Any TEAE
 - Maximum severity: Mild
 - Maximum severity: Moderate
 - Maximum severity: Severe
- At least one related TEAE
- At least one serious TEAE
- Subjects discontinued due to a TEAE
- Serious treatment-emergent adverse events (TESAEs)
- Died on study.

Additionally, n (%) are calculated based on the number of unique subjects within each MedDRA category (e.g., preferred term) by treatment group. A subject reporting multiple events of the same category will be counted only once for that category. For summary purposes, AE relationship to the iovera^o or RFA will be grouped into “Unrelated” for “unrelated” or “unlikely related” and “Related” for “possible”, “probably”, or “definite”. For subjects with more than one event coded to the same PT, the subjects will be counted for the categories with the strongest relationship and the greatest severity. The following subject incidence tables will be presented:

- TEAEs by PT (Preferred Term) sorted by the decreasing order of subject incidence in the combined group
- TEAEs by SOC (System Organ Class) and PT sorted alphabetically
- TEAEs treatment-related by SOC and PT
- TEAEs by severity and by SOC and PT

- TESAEs by SOC and PT.

A data listing will be provided for all AEs. Included in the listing are the reported term, PT, SOC, TEAE and TESAE flag, study day when AE starts, duration, relationship to treatment(s), severity, action taken, outcome, and seriousness category.

Separate data listings will be provided for subjects who experience SAEs and die on study.

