9.7.2.1. Primary Efficacy Analysis

9.7.2.1.1. NRS "average pain over past 24 hours" Intensity Score scores from first pain assessment post-treatment (Day 1) to Day 360

The primary analysis of the primary efficacy endpoint will compare the iovera^o and RFA group. The superiority of iovera^o to RFA will be evaluated based on the following null hypothesis and alternative hypothesis:

H₀: iovera^o is not superior to RFA with respect to mean of NRS pain intensity scores at Day 360

H_a: iovera^o is superior to RFA with respect to mean of NRS pain intensity scores at Day 360

A two-sided hypothesis test will be performed at $\alpha=0.05$ level of significance comparing EXPAREL and bupivacaine HCl as follows:

- If the two-sided p-value for the least squares mean treatment difference in NRS at Day 360 (iovera^o- RFA) is >0.05 , then the superiority of iovera^o to RFA is not achieved.
- If the p-value for the least squares mean treatment difference in NRS at Day 360 (iovera^o- RFA) is ≤ 0.05 , then the superiority of iovera^o to RFA is achieved.

Least Squares Means (LSM) of “average pain over 24 hours” at Day 360 will be calculated for each subject. LSM for “average pain over 24 hours” at Day 360 will be summarized by treatment group, and overall.

To test for significant differences between iovera^o and RFA group, a Linear Regression Model with adjustment of baseline NRS, sex, and tobacco status was used. The LS means for each treatment group, two-sided 95% CI for the LS mean difference, and p-value will be presented.

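### In the readable SAP every confidence interval is on an efficacy outcome, while the safety and completion rates that serve the primary objective have none

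*SAP*

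**What the plan says.** SAP 5.1 opens with "The primary objective of this study is to assess the safety and feasibility of" iovera cryoneurolysis compared with RFA, and the protocol synopsis states the same objective. SAP 10 sets the size: "A total of 30 subjects are planned for this pilot study, with 15 randomized to each of the 2 study groups". It adds that "sample size will not be calculated based on desired statistical power to detect a treatment effect", and says that assessing efficacy is not the aim.

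For safety, SAP 9.6 says "Safety data will be summarized descriptively by treatment groups and overall" and then "No statistical testing for comparison of treatment groups will be performed for safety variables". The protocol's Statistical Methods section agrees. In SAP 9.6.1, "AEs will be summarized using subject incidence table", and of the overview table it says "This table will include n (%) of subjects with" each listed type of event. SAP 9.6.2 summarizes device-caused death, serious injury and malfunction as incidences per group. SAP 9.2 lists numbers randomized and completed. The general rule in SAP 9.1 for categorical data is number and percentage, and by default only categories that occur in the data are shown. The safety denominator (SAP 8) is the subjects treated, by treatment actually received.

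For efficacy, SAP 9.7.2.1.1 asks for LS means, a p-value and a "two-sided 95% CI for the LS mean difference" in NRS average pain. SAP 9.7.2.2 applies the same presentation to NRS at Days 30, 180 and 360, percent change in NRS, ODI, change in ODI, and PGIC.

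**The concern.** The plan states precision for outcomes that it says are not the study's aim, and states none for the rates that serve its primary objective. The study is meant to show whether a full trial can be run with these procedures, and to give a basis for its sample size. Both uses depend on how uncertain a rate is as well as on its observed value. In an arm of 15, a count of zero or one looks reassuring as a percentage but is weak evidence that the true rate is low. If the tables carry no interval, nothing in the planned output tells the reader so.

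**Working it through.** **Plan's own figure.** The only figure to reproduce is the sample size: 2 × 15 = 30, which agrees. No event rate, precision target or power is given, so there is no further calculation to check.

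**Where intervals are specified in the readable text.**

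| Outcome | SAP section | Form | Interval |
|---|---|---|---|
| NRS average pain, Day 360 | 9.7.2.1.1 | LS mean difference | Two-sided 95% |
| NRS at other days, % change in NRS, ODI, change in ODI, PGIC | 9.7.2.2 | As for the primary analysis | Same, by reference |
| Adverse event rates | 9.6.1 | Count and percentage | None |
| Device death, serious injury, malfunction | 9.6.2 | Incidence | None |
| Completion | 9.2 | Number of subjects | None |

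**Inputs.** n = 15 per arm and 30 overall (SAP 10), taking all planned subjects as treated. The event counts and true rates below are assumptions for illustration, because the documents give none.

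**Zero events.** The exact (Clopper-Pearson) two-sided 95% upper limit is 1 − 0.025^(1/n).
- n = 15: 1 − 0.025^(1/15) = 21.8%
- n = 30: 1 − 0.025^(1/30) = 11.6%

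If only 12 to 14 subjects in an arm were treated, the limit for zero events would be 26.5% to 23.2%.

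**Other counts.** For x events in n, the lower limit is the 2.5% quantile of Beta(x, n − x + 1) and the upper limit is the 97.5% quantile of Beta(x + 1, n − x).

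| Events | Observed | Exact 95% CI |
|---|---|---|
| 1/15 | 6.7% | 0.2% to 31.9% |
| 2/15 | 13.3% | 1.7% to 40.5% |
| 3/15 | 20.0% | 4.3% to 48.1% |

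Completion of 12/15 (80%) is the complement of 3/15, so its interval runs from 100 − 48.1 = 51.9% to 100 − 4.3 = 95.7%.

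**Chance of seeing no event at all.** This is (1 − p)^n for a true rate p.
- p = 10%: 0.9^15 = 0.206 in one arm; 0.9^30 = 0.042 over both arms
- p = 5%: 0.95^15 = 0.463 in one arm; 0.95^30 = 0.215 over both arms

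**Sensitivity to method.** For 0/15 the upper limit is 20.4% by Wilson, 18.1% by the one-sided 95% exact method, and 3/15 = 20% by the rule of three. The choice of method does not change the conclusion.

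**The case against.** The strongest reply is that this is a reporting preference. The protocol and SAP agree that safety is descriptive, which is usual in a pilot. Nothing is contradictory and no data are lost. The count appears beside each percentage and an overall summary is planned, so any reader can derive the interval, even after the trial. That reply limits the severity of the point but does not remove it. The SAP says that it sets out the analyses on which conclusions will be based, and it did not treat small size as a reason to leave intervals off efficacy. The bar in SAP 9.6 is on testing between groups. An interval within one arm tests nothing.

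Three stronger readings are tempting, and the documents do not support them.

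- A reader might infer that the decision to proceed to a full trial will rest on point estimates such as 0/15. This cannot be known. The adverse event stopping rules in SAP 9.6.3 and all of SAP 9.6.4 on study success are redacted, and the protocol's list of feasibility outcomes is not visible. Any of these could hold a threshold or an interval.
- A reader might infer that the plan contains a single confidence interval. It is written out once, but SAP 9.7.2.2 carries it to several secondary endpoints.
- A reader might infer that every event type with no cases will be printed as 0%. Under SAP 9.1 a preferred term with no cases in either arm would by default not appear at all. A printed 0% would arise mainly in the overview lines or where the other arm had a case.

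It is also fair to say that the 10% rate and the 12/15 completion are illustrations, and that the readable text sets no rate as clinically important.

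**Conclusion.** The point holds for the readable text as an inexpensive improvement. It is not an error that invalidates the analysis. All specified intervals are on efficacy outcomes, and the safety and completion rates behind the primary objective have none. The missing information is large at this size: with 15 treated, zero events leaves true rates up to 21.8% open, and with 30 up to 11.6%. The figure for 30 describes a mixture of two procedures, so it does not replace the per-arm limit for iovera.

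These figures assume that all 30 planned subjects are treated, 15 with each procedure; fewer treated would widen them. The verdict also assumes that the redacted sections do not already supply intervals. If they do, the tables described in 9.6.1 and 9.6.2 would still need to show them.

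**What to change.** **First settle the numerators.** SAP 7 and one sentence of SAP 9.6.1 count adverse events from the start of iovera treatment only, while another sentence of 9.6.1 covers iovera or RFA. Read literally, the first two give the RFA arm no start point. Use one definition: onset on or after the start of the study treatment received, in either arm. In 9.6.2, also reconcile the definition of an adverse device effect, which applies whether or not the event is related to the device, with the summary, which is limited to events resulting from the device.

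**Then add intervals.**
- In 9.6.1 and 9.6.2, give exact (Clopper-Pearson) two-sided 95% intervals, by arm and overall, for: at least one related TEAE, at least one serious TEAE, discontinuation due to a TEAE, any serious adverse device effect, and any device malfunction.
- Keep these as fixed rows even when the count is zero, as a stated exception to the display rule in 9.1, and report the upper limit in the text.
- Add the same interval to the completion rate in 9.2.
- Add no between-arm test.

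**Cost.** A few extra columns in tables already planned, with no new data and no additional subjects. The downside is that the reported safety result will look less favourable than counts and percentages alone.
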